## 7 Technical Aspects

### 7.1 Study Agent Preparation

We propose to purchase EGCG from Beehive Botanicals. Beehive Botanicals, Inc. has the capacity to formulate and manufacture vegetable capsules containing 200mg of Green Tea extract. Beehive Botanicals is NSF certified as a cGMP facility. Per Beehive SOPs, all incoming material is third party tested for identity and potency to confirm compliance with Certificates of Authentication (COA). The material per the COA has a shelf life of 3 years in correct holding conditions. Clomiphene citrate and letrozole will be obtained through generic pharmaceutical companies.

The study coordinator at each site will be responsible for distributing the supply drug kits, verifying pill/vial counts, and determining that there are adequate medication supplies for existing patients and new patients to be randomized. The PI will ultimately be accountable for administration and accountability of the medication used in this study.

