### 3 Background and Significance

#### 3.1 Overview

Uterine leiomyomas (fibroids) affect 30-50% of reproductive-age women and are a significant cause of infertility. Intramural and submucosal fibroids reduce the likelihood of pregnancy (RR=0.3-0.7) compared to unaffected women. Surgical removal of fibroids can restore fertility; however, recurrence rates are high, and benefits are often temporary. Importantly, serious postoperative consequences such as adhesions can adversely affect a woman's fertility and health in general. Hormonal therapies that induce medical menopause can be used to reduce fibroid size, but these therapies also prevent pregnancy. There is a critical need for effective, non-hormonal, non-surgical fertility treatment options for women with fibroids that may distort the uterine cavity. Our long-term goal is to develop novel non-hormonal treatments for uterine fibroids. Green Tea leaves contain polyphenols and catechins, such as epigallocatechin gallate (EGCG). Studies from our group and others have shown that EGCG is the most abundant and active compound responsible for effects of Green Tea extracts. Notably, EGCG can be taken during pregnancy and there are no known teratogenic effects. EGCG polyphenols inhibit key pathways of tumor growth by modulating signaling pathways involved in cell proliferation, transformation, inflammation, apoptosis, metastasis and invasion. Prior to initiating a randomized, double-blind, multi-center, prospective, clinical trial of EGCG versus placebo in women with uterine fibroids to evaluate birth rate a pharmacokinetic and hepatic safety analysis must be conducted. The pharmacokinetics and hepatic safety of EGCG with clomiphene citrate and letrozole are unknown. A 3-arm study will be conducted in women with and without fibroids to allow comparisons between these groups. The results of this study will be used to confirm hepatic safety for the larger multi-center FRIEND study.

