### **3.3 EGCG Clinical trial in women with symptomatic uterine fibroids**

To translate the positive EGCG anti-fibroid preclinical findings in human fibroid cell lines and fibroid animal models, the efficacy and safety of EGCG on uterine fibroids burden and quality of life in women with symptomatic uterine fibroids were evaluated in an NIH-funded double-blinded, placebo-controlled randomized clinical trial(NCT 01311869) (1). A total of 39 reproductive-age women (age 18–50 years, day 3 serum follicle-stimulating hormone <12 IU/L) with symptomatic uterine fibroids were recruited for this study. All subjects had at least one fibroid lesion 2 cm^3 or larger in volume, as confirmed by transvaginal or transabdominal ultrasonography. The subjects were randomized to oral daily treatment with either 800 mg of decaffeinated EGCG or placebo (800 mg of brown rice) for 4 months, and uterine fibroid volumes were measured at the end of study, also by transvaginal or transabdominal ultrasonography. The fibroid-specific symptom severity and HRQL of these uterine fibroid patients were scored at each monthly visit, using the symptom severity and quality-of-life questionnaires (1). Of the final 39 women recruited for the study, 33 completed all five visits of the study. In the placebo group (n = 11), fibroid volume increased (24.3%) over the study period; however, patients randomized to green tea extract treatment (n = 22) showed significant reduction (32.6%, P = 0.0001) in total uterine fibroids volume. In addition, EGCG treatment significantly reduced fibroid-specific symptom severity (32.4%, P = 0.0001) and induced significant improvement in HRQL (18.53%, P = 0.01) compared to the placebo group. Anemia also significantly improved by 0.7 g/dL (P = 0.02) in the EGCG treatment group, while average blood loss significantly decreased (P = 0.001). No adverse effects, endometrial hyperplasia, or other endometrial pathology were observed in either group (1).

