#### 4.3.2 Study Population

Thirty-six (36) patients will be equally randomized via computer-generated randomization schedule to receive:

1. Two capsules of decaffeinated Green Tea extract (close to 800mg EGCG) taken orally on a daily basis for up to 2 months
2. Two capsules of decaffeinated Green Tea extract taken orally on a daily basis for up to 2 months with clomiphene citrate 100mg for 5 days
3. Two capsules of decaffeinated Green Tea extract taken orally on a daily basis for up to 2 months with letrozole 5mg for 5 days.

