#### 4.4.2 Possible risks/discomforts

Blood draws: Discomfort, bruising, infection or bleeding at the needle puncture site

Pelvic ultrasound: abdominal or pelvic discomfort

EGCG: Gastrointestinal upset; rare liver toxicity. The literature supports a potential relationship between high-dose Green Tea extract consumption and transient changes in serum liver enzymes. Rare ( $<5\%$ ) and transient liver transaminase elevations have been documented. Hepatotoxicity tended to show a temporal relationship between Green Tea extract consumption and effect onset with Green Tea extract-induced toxicity mainly manifesting after roughly 3-4 months of consumption. Daily intake of 1315 mg of Green Tea catechins containing 843 mg EGCG poses mainly mild, transient hepatic adverse effects. The incidence and severity of hepatotoxicity increased when Green Tea extract or EGCG was administered under fasted conditions, while exposure to Green Tea under fed conditions appears to alleviate such risk.

Clomiphene Citrate: Visual changes (such as blurring of vision, double vision, floaters), abdominal pain, nausea, vomiting, constipation, mood changes, headache, hot flashes, fatigue, abnormal endometrial thickening, multiple pregnancies, formation of ovarian cyst, breast discomfort, abnormal uterine bleeding, and bloating

Letrozole: Fatigue, dizziness, nausea, hot flashes, arthritis pain in your joints, back pain, increased cholesterol levels, formation of ovarian cysts, multiple pregnancies

Other risks: There is also the risk of loss of confidentiality. Filling out the questionnaires may make the subjects uncomfortable or feel some anxiety. There is a risk that information about the subject may become known to people outside of this study.

As this is a NIH (NICHD) funded study, your study information is protected by a Certificate of Confidentiality. This Certificate allows us, in some cases, to refuse to give out your information even if requested using legal means.

It does not protect information that we have to report by law, such as child abuse or some infectious diseases. The Certificate does not prevent us from disclosing your information if we learn of possible harm to yourself or others, or if you need medical help.

Disclosures that you consent to in this document are not protected. This includes putting research data in the medical record or sharing research data for this study or future research. Disclosures that you make yourself are also not protected.

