## 5.5 Randomization/Treatment Initiation

Thirty-six (36) patients will be equally randomized via computer-generated randomization schedule to receive: 1) 800 mg of decaffeinated EGCG taken orally on a daily basis with food for up to 2 months; 2) 800 mg of decaffeinated EGCG taken orally on a daily basis with food for up to 2 months with clomiphene citrate 100mg for 5 days; 3) 800 mg of decaffeinated EGCG taken orally on a daily basis with food for up to 2 months with letrozole 5mg for 5 days.

Treatment assignments will be randomized for age groups and presence of fibroids by a varying-block-size design. The DCC statisticians will generate the randomization scheme for the study.

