### 6.2 Primary Outcome Measurements

The primary outcome parameter will be differences in pharmacokinetic parameters of EGCG and 2 of the major metabolites between the 3 treatment groups.

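### The only capsule strength in the protocol (200 mg of extract) cannot give about 800 mg EGCG from two capsules a day

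*Combined protocol and SAP*

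**What the plan says.** Section 4.3.2 defines the first arm as "Two capsules of decaffeinated Green Tea extract (close to 800mg EGCG) taken orally on a daily basis for up to 2 months". The other two arms take the same two capsules with clomiphene citrate or letrozole added for five days. Section 5.5 gives the regimen by mass, in the same terms for each arm: "800 mg of decaffeinated EGCG taken orally on a daily basis with food for up to 2 months". These two sections agree with each other. They also match the earlier fibroid trial summarised in section 3.3, which used "oral daily treatment with either 800 mg of decaffeinated EGCG or placebo (800 mg of brown rice) for 4 months".

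Section 7.1 describes the product. It says "We propose to purchase EGCG from Beehive Botanicals" and then that this supplier "has the capacity to formulate and manufacture vegetable capsules containing 200mg of Green Tea extract". No other section gives a capsule strength, the EGCG content of the extract, or a different number of capsules.

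Two further statements show what depends on the dose. The primary outcome in section 6.2 is "differences in pharmacokinetic parameters of EGCG and 2 of the major metabolites between the 3 treatment groups". Section 3.1, repeated in section 5.2, says "The results of this study will be used to confirm hepatic safety for the larger multi-center FRIEND study".

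**The concern.** Two capsules can supply 800 mg EGCG only if each holds 400 mg EGCG. A capsule filled with 200 mg of extract cannot do that, because EGCG is one component of the extract. So the product described in 7.1 and the regimen in 4.3.2 and 5.5 cannot both be right as written.

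The study exists to describe the pharmacokinetics and hepatic safety of EGCG, and a liver safety result can be interpreted only at a known dose. If the 7.1 capsule were dispensed two a day, a clean liver result would be credited to at least twice the dose taken, which is the unsafe direction of error. Absolute EGCG exposure would carry the same wrong label.

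The routine checks would not clearly reveal this. Adherence is judged by pill counts, which would look perfect at two a day. The third-party testing in 7.1 compares incoming material with its certificate, not with the protocol dose.

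**Working it through.** **Inputs from the protocol**

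- Capsules per day: n = 2 (4.3.2)
- Daily EGCG dose: 800 mg (5.5; 4.3.2 says close to this)
- Extract per capsule: m = 200 mg (7.1)
- EGCG dose cited in the risk section: 843 mg a day (4.4.2)

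**Input not in the protocol**

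- EGCG fraction of the extract, f. It is not given, but it cannot exceed 1.

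**Formula:** daily EGCG = n × m × f.

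1. *Trying to reproduce the stated dose.* EGCG needed per capsule is 800 / 2 = 400 mg. Against the 7.1 capsule this is 400 / 200 = 2.0, so EGCG would have to be 200% of the capsule's extract. The stated dose cannot be reproduced from the stated capsule for any possible f.

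2. *Ceiling.* With f = 1, which also covers reading the 200 mg as pure EGCG, daily EGCG = 2 × 200 × 1 = 400 mg. That is 400 / 800 = 50% of the stated dose. The words allowing an approximate dose in 4.3.2 cannot absorb a factor of two.

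3. *Capsules needed.* With f = 1, 800 / 200 = 4 capsules a day. A lower f needs more.

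4. *Range over f.* The fractions below 1 are assumptions for illustration.

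| Assumed f | Daily EGCG from two capsules (400 × f) | Share of 800 mg |
|---|---|---|
| 1.0 | 400 mg | 50% |
| 0.75 | 300 mg | 37.5% |
| 0.5 | 200 mg | 25% |

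5. *Against the cited hepatic dose.* Section 4.4.2 states: "Daily intake of 1315 mg of Green Tea catechins containing 843 mg EGCG poses mainly mild, transient hepatic adverse effects". The labelled dose is 800 / 843 = 95% of that EGCG intake; the ceiling from two 7.1 capsules is 400 / 843 = 47%. The label would place this study close to the dose for which hepatic effects are cited, while the intake could be less than half of it.

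**The case against.** The strongest reply is that 7.1 is not a product specification. It says what the supplier is able to make and what the investigators propose to buy. It does not say that the 200 mg capsule is dispensed, or that no other strength is made. The dosing sections agree with each other and imply about 400 mg EGCG per capsule, so the dose instruction is not undefined, and the supply sentence may simply be loose or out of date. This stands as far as underdosing goes: the documents do not show that anyone received less than 800 mg. It does not remove the mismatch. If the study capsule is a different one, 7.1 describes the wrong product and the true strength is stated nowhere, so a correction is needed either way.

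A second reply is that the consequences are limited. All arms take the same EGCG regimen, so the between-arm comparison in 6.2 is largely protected; that stands. EGCG and its metabolites are also measured in blood, over eight hours at Visits 1 and 2, so exposure is observed whatever the label says. That is true of the concentrations, but not of the dose they are reported against.

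A third reply is that the larger trial's dose is not given. If it used the same capsules at the same count, the safety result would carry over in practice. That is possible, but nothing in the documents establishes it.

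**Conclusion.** The concern holds and should be fixed. The only capsule strength in the protocol does not fit the dose of two capsules a day for about 800 mg EGCG. If that capsule is the one dispensed, the daily EGCG dose is at most 400 mg, and the dose label on absolute pharmacokinetics and liver safety is too high by a factor of at least two.

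The ceiling rests only on the protocol's own figures and on the fact that a component cannot outweigh the whole. The lower values in the range rest on assumed purity. Whether the 7.1 capsule is the study capsule, and which of the figures is wrong, cannot be settled from the documents.

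**What to change.** Check the certificate and label of the capsules actually supplied. Then correct 7.1 to give mg of extract and mg of EGCG per capsule as separate figures, or correct the capsule count in 4.3.2. Capsules per day × mg EGCG per capsule should equal the daily EGCG dose in 4.3.2 and 5.5, for all three arms.

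If the supplied capsules deliver less than 800 mg from two a day, either change the count or restate the dose to which the pharmacokinetic and liver safety results apply.

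The cost is low: one certificate and label check, and a wording correction sent by numbered memo under 7.11. Amendments also go to the single IRB under 7.9. A change to dosing or to the stated dose is needed only if the check shows a shortfall.

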### 7.2 Concomitant Medications

An inquiry into concomitant medications will be made at the screening visit as well as each subsequent visit.

### 7.3 Adverse Experience Reporting

#### 7.3.1 Adverse Events

##### 7.3.1.1 Definition of Adverse Events (AE)

Adverse event means any untoward medical occurrence associated with the use of an intervention in humans, whether or not considered intervention-related (21 CFR 312.32 (a)).

##### 7.3.1.2 Definition of Serious Adverse Events (SAE)

An adverse event (AE) or suspected adverse reaction is considered "serious" if, in the view of either the investigator or sponsor, it results in any of the following outcomes: death, a life-threatening adverse event, inpatient hospitalization or prolongation of existing hospitalization, a persistent or significant incapacity or substantial disruption of the ability to conduct normal life functions, or a congenital anomaly/birth defect. Important medical events that may not result in death, be life-threatening, or require hospitalization may be considered serious when, based upon appropriate medical judgment, they may jeopardize the participant and may require medical or surgical intervention to prevent one of the outcomes listed in this definition.

#### 7.3.2 Classification of an Adverse Event

##### 7.3.2.1 Severity of Event

The following guidelines will be used to describe severity.

- **Mild** – Events require minimal or no treatment and do not interfere with the participant's daily activities.

- **Moderate** – Events result in a low level of inconvenience or concern with the therapeutic measures. Moderate events may cause some interference with functioning.
- **Severe** – Events interrupt a participant’s usual daily activity and may require systemic drug therapy or other treatment. Severe events are usually potentially life-threatening or incapacitating. Of note, the term “severe” does not necessarily equate to “serious”.

### **7.3.2.2 Relationship to Study Intervention**

All adverse events (AEs) must have their relationship to study intervention assessed by the clinician who examines and evaluates the participant based on temporal relationship and his/her clinical judgment. The degree of certainty about causality will be graded using the categories below. In a clinical trial, the study product must always be suspect.

- **Definitely Related** – There is clear evidence to suggest a causal relationship, and other possible contributing factors can be ruled out. The clinical event, including an abnormal laboratory test result, occurs in a plausible time relationship to study intervention administration and cannot be explained by concurrent disease or other drugs or chemicals. The response to withdrawal of the study intervention (dechallenge) should be clinically plausible. The event must be pharmacologically or phenomenologically definitive, with use of a satisfactory rechallenge procedure if necessary.
- **Probably Related** – There is evidence to suggest a causal relationship, and the influence of other factors is unlikely. The clinical event, including an abnormal laboratory test result, occurs within a reasonable time after administration of the study intervention, is unlikely to be attributed to concurrent disease or other drugs or chemicals, and follows a clinically reasonable response on withdrawal (dechallenge). Rechallenge information is not required to fulfill this definition.
- **Potentially Related** – There is some evidence to suggest a causal relationship (e.g., the event occurred within a reasonable time after administration of the trial medication). However, other factors may have contributed to the event (e.g., the participant’s clinical condition, other concomitant events). Although an AE may rate only as “possibly related” soon after discovery, it can be flagged as requiring more information and later be upgraded to “probably related” or “definitely related”, as appropriate.
- **Unlikely to be related** – A clinical event, including an abnormal laboratory test result, whose temporal relationship to study intervention administration makes a causal relationship improbable (e.g., the event did not occur within a reasonable time after administration of the study intervention) and in which other drugs or chemicals or underlying disease provides plausible explanations (e.g., the participant’s clinical condition, other concomitant treatments).
- **Not Related** – The AE is completely independent of study intervention administration, and/or evidence exists that the event is definitely related to another etiology. There must be an alternative, definitive etiology documented by the clinician.

### **7.3.2.3 Expectedness**

The study PI will be responsible for determining whether an AE is expected or unexpected. An AE will be considered unexpected if the nature, severity, or frequency of the event is not consistent with the risk information listed in the package insert, or in the consent form.

### *7.3.3 Time Period and Frequency for Event Assessment and Follow-up*

The occurrence of an AE or serious adverse event (SAE) may come to the attention of study personnel during study visits and interviews of a study participant presenting for medical care, or upon review by a study monitor.

All AEs including local and systemic reactions not meeting the criteria for SAEs will be captured on the appropriate case report form (CRF). Information to be collected includes event description, time of onset, clinician's assessment of severity, relationship to study product (assessed only by those with the training and authority to make a diagnosis), and time of resolution/stabilization of the event. All AEs occurring while on study must be documented appropriately regardless of relationship. All AEs will be followed to adequate resolution.

Any medical condition that is present at the time that the participant is screened will be considered as baseline and not reported as an AE. However, if the study participant's condition deteriorates at any time during the study, it will be recorded as an AE.

Changes in the severity of an AE will be documented to allow an assessment of the duration of the event at each level of severity to be performed. AEs characterized as intermittent require documentation of onset and duration of each episode.

Site personnel will record all reportable events with start dates occurring any time after informed consent is obtained until 7 (for non-serious AEs) or 30 days (for SAEs) after the last day of study participation. At each study visit, the investigator will inquire about the occurrence of AE/SAEs since the last visit. Events will be followed for outcome information until resolution or stabilization.

### *7.3.4 Adverse Event Reporting*

Adverse events deemed non-serious will be recorded throughout study participation from the start of study drug through one week after the last dose of study medication and reported to the DCC. Non-serious adverse events will be reported to the DSMB quarterly.

Supervising Institutional Review Boards (IRBs) will be notified by local investigators of adverse events occurring at their institution according to their reporting requirements. Investigators also will notify the medical monitor and DCC within 24 hours after knowledge of a death or of an event that is life-threatening, that results in hospitalization or prolongation of hospitalization, or that involves a persistent or significant disability or incapacity. Study staff will collect information regarding the treatment provided, outcome, and presumed relationship to study, and a narrative description of the event. The study staff will provide updated reports to the DCC as new information becomes available. DCC personnel will review the data and query the clinical sites for clarification and additional information. In addition, the DCC will provide the information to the Data and Safety Monitoring Board (DSMB) as part of their safety review.

The DCC will provide study-wide summary statistics (not filtered by treatment group) of adverse events to the single IRB annually and upon request to all sites on an annual basis for submission to their IRBs.

